13.8 Whole body $^{18}\text{FDG-PET}$ Scan

Tumor assessments will be done via whole body $^{18}\text{FDG-PET}$ scan.

The investigator will check the patient's fasting blood glucose prior to the ¹⁸FDG-PET scan and ensure that the fasting blood glucose is below 200 mg/dL. The investigator should also ensure that the patient is able to lie down for 60 minutes.

13.9 Exploratory Studies

Exploratory analyses will be conducted on stored tissues and blood at a later time to investigate molecular profiling of the tumors using cytogenetics (using fluorescence in situ hybridization or FISH), gene profiling by New Genome Sequence (NGS) or other molecular techniques. Finally, CTCs will be analyzed at the same time points as those for the analysis of the biological effects, and will be determined during Cycle 1 only.

A comprehensive analysis of NK cell function may require as little as 3.5 ml of heparinized whole blood. We will conduct similar analysis in tissue samples. This will help in the characterization of NK cell subsets and assessment of NK cell activation in the peripheral blood. In addition, phenotypic and functional characterization of other immune cells, including T cells, MDSCs, Tregs and tumor cell surface and internal proteins identification and their role in specific pathways may be explored to gain potential insights into the key biochemical and molecular drivers of response or resistance to AFM13 therapy.

Anti-drug antibodies will be analyzed at an Affimed-contracted laboratory facility in UK.

These assessments and the assessment schedule are described in detail in the Immunobiology Research Manual.

14 ASSESSMENT OF SAFETY

The timing and frequency of safety assessments are described in Section 9.5.

All patients will be evaluated for safety if they have received any study drug. The start and stop time of each AFM13 infusion must be documented. Toxicity assessments will be continuously performed during the treatment phase. Some of the assessments listed below may not be captured as data in the CRF. They are intended to be used as safety monitoring by the treating physician. Additional testing or assessments may be performed as clinically indicated.

14.1 Adverse Events

Definitions

The definitions for AEs and SAEs are given below. It is of the utmost importance that all staff involved in the study is familiar with the content of this section. The principal investigator is responsible for enduring this.

Evaluable for toxicity.

All patients who have received at least one dose of study drug will be evaluable for toxicity starting from Day 1 of Cycle 1.

Adverse Event

An AE is defined as any untoward medical occurrence in a subject, or clinical investigation subject administered a pharmaceutical product, and which does not necessarily have a causal relationship with this treatment. An AE can therefore be any unfavorable and unintended sign, symptom or disease temporally associated with the use of a medicinal (investigational) product, whether or not related to the medicinal (investigational) product.

Adverse Reaction

An adverse reaction is any detrimental and unintentional reaction to an investigational drug, independent of the administered dose.

Serious Adverse Event

An SAE is defined as, but is not limited to, one that:

- Results in death
- Is life-threatening (Report if suspected that the patient was at substantial risk of dying at the time of the adverse event, or use or continued use of the device or other medical product might have resulted in the death of the patient.)
- Requires in-patient hospitalization or prolongs existing hospitalization
- Results in persistent or significant disability/incapacity
- Is a congenital anomaly/birth defect

Important medical events that may not result in death, be life-threatening or require hospitalization may be considered a serious adverse drug experience, when based on appropriate medical judgment, they may jeopardize the subject or the subject may require medical or surgical intervention to prevent one of the outcomes listed in this definition.

A hospital stay is any stay in a hospital as an in-patient for at least one night. A hospitalization that has already been planned before the first administration of the investigational drug is not considered as an SAE.

14.2 Unexpected Adverse Reaction

An unexpected adverse reaction is an adverse reaction that does not correspond to the existing investigator brochure detailed information on the investigational drug in terms of the nature and severity of this reaction.

The existing information on the investigational product is stated in the current version of the AFM13 IB, which is to be used as a reference.

14.3 Suspected Unexpected Serious Adverse Reaction

A suspected unexpected serious adverse reaction (SUSAR) is a case in which the occurrence of a serious adverse reaction that could not be expected is suspected (there is a certain or possible relation to the administered protocol medication), and the nature and severity of this reaction do not correspond to the existing information on the respective investigational drug. The reaction is rated as serious and a relation between the investigational drug and the reaction is considered to be possible. If the relation between adverse reaction and protocol medication is not evaluable or not evaluated, the relation is regarded as possible in context of the SUSAR. The existing information on the respective investigational drug can be found in the IB.

14.4 Causality/Relationship

For each event that occurs, an assessment of causality has to be performed.

- Not Evaluable
It is not possible to assess whether there is a relation with the administered investigational drug(s) or not.
- Not Evaluated
An event that was reported as AE, but for which a relation with the administered investigational drug(s) was not established at the time of reporting because further data were necessary or is currently being compiled.
- No Relation
An event on which there is sufficient information available to assume that there is no relation with the investigational drug.
- Possible Relation

An event that follows a matching chronological course after administration of the investigational drug, or that follows a known or expected scheme of response to the suspect investigational drug, but which could also have been caused by a number of other factors.

- **Probable Relation**

An event that follows a matching chronological course after administration of the investigational drug, or that follows a known or expected scheme of response to the suspect investigational drug, and that disappears after the administration is discontinued or reduced to a lower dose, and that cannot be explained by the known clinical condition of the patient.

- **Certain Relation**

An event that follows a matching chronological course after administration of the investigational drug, or an event due to which the concentration of the investigational drug in the body tissues or fluids is measured, that follows a known or expected scheme of response to the suspect investigational drug, and that disappears after the administration is discontinued or reduced to a lower dose and reappears after repeated exposure.

14.5 Recording of Adverse Events

For the purposes of this study, any detrimental change in the patient's condition, after signing the informed ICF and up to completion of the EOS assessments should be considered an AE.

Adverse events will be recorded the signing of informed consent until the EOS visit.

Every grade 3/4 AE must be documented, independent of the investigator's opinion whether there is a causative relation with therapy or not.

Unexpected AEs are to be documented on the respective CRF form (AE form). Documentation includes the nature of the event, beginning, duration, intensity/stage and causality.

All AEs have to be tracked until they have subsided or stabilized.

All AEs that are not rated as unexpected have to be documented.

All ongoing AEs should be followed up for 30 days after the last administration of study drug, with the exception of any ongoing study drug-related AEs, which should be followed until resolution, unless in the investigator's opinion, the AE is unlikely to resolve due to the patient's underlying disease. Any new SAEs occurring up to 60 days after the last administration of study drug should be reported to *spm² – safety projects & more GmbH*, the Affimed 's safety Clinical Research Organization (CRO) according to Section 14.3

At any time after the follow-up visit, if an investigator learns of an SAE that can be reasonably related to study drug, he/she should promptly notify the IRB/EC and FDA according to institutional and federal guidance, respectively. Affimed's safety *CRO spm²* shall also be notified. The reports will be sent to

spm² – safety projects & more GmbH
[name]
Safety [contact]
Email: [contact]

The investigator will assess the degree of severity as follows:

- mild
- moderate
- severe
- immediately life-threatening

The evaluation is to be based on the official CTCAE version 4.0.

It is important to distinguish between serious and severe AEs. Severity is a measure of intensity whereas seriousness is defined by the criteria in Section 14.

An AE of severe intensity need not necessarily be considered serious. For example, nausea that persists for several hours may be considered severe nausea, but not an SAE. On the other hand, a stroke that results in only a limited degree of disability may be considered a mild stroke but would be an SAE.

For an AE to be a suspected drug-related event, there should be at least a reasonable possibility of a causal relationship between the study drug and the AE.

14.6 Expedited Adverse Event Reporting

The Principal Investigator agrees to provide appropriate parties with copies of all serious adverse events within two working days. Reportable information should always be reported by the Principal Investigator directly to the IRB within 5 working days from when the Principal Investigator learns of the event or new information. Additionally, the Principal Investigator agrees to report any pregnancy occurring in association with use of study drug to the appropriate parties.

Serious adverse events (SAE) are defined above. The investigator must inform spm² in writing using a spm² SAE form or MEDWATCH 3500A form of any SAE within 24 hours of being aware of the event. The written report must be completed and supplied to spm² by facsimile within 24 hours/1 business day. The initial report must be as complete as possible, including an assessment of the causal relationship between the event and the investigation product, if available. Information not available at the time of the initial report (e.g., an end date for the adverse event or laboratory values received after the report) must be documented on a follow-up report. A final report to document resolution of the SAE is required. The institutional protocol number should be included on the SAE reports (or on the fax cover letter) sent to

spm². A copy of the fax transmission confirmation of the SAE report to spm² should be attached to the SAE and retained with the patient records

NAME OF SAE REPORTING
ADDRESS (as appropriate)
spm ² – safety projects & more GmbH [name] Safety [contact] Email: [contact]

The investigator is responsible for reporting any SAEs to the FDA. **Serious AEs** that are **unlisted/unexpected, and at least possibly associated to the drug**, and that have not previously been reported in the IB, or reference safety information document should be reported promptly to the FDA by [contact]), fax ([name]), or via MedWatch Online. Fatal or life-threatening SAEs that meet the criteria for reporting to the FDA must be reported to the FDA within 7 calendar days after awareness of the event. All other SAEs that meet the criteria for reporting to the FDA must be reported to the FDA within 15 calendar days after awareness of the event. A clear description of the suspected reaction should be provided along with an assessment as to whether the event is drug or disease related.

Note: All deaths on study require expedited reporting regardless of causality. Attribution to treatment or other cause must be provided.

Expedited AE Reporting Timelines

One business day; 5 calendar days – The investigator must initially report the AE within 1 business day of learning of the event followed by a complete report within 5 calendar days of the initial 24-hour report.

10 calendar days - A complete report on the AE must be submitted within 10 calendar days of the investigator learning of the event.

Any medical event equivalent to CTCAE grade 3, 4, or 5 that precipitates hospitalization (or prolongation of existing hospitalization) must be reported regardless of attribution and designation as expected or unexpected with the exception of any events identified as protocol-specific expedited AE reporting exclusions.

Any event that results in persistent or significant disabilities/incapacities, congenital anomalies, or birth defects must be reported if the event occurs following treatment.

14.7 Adverse Event Updates/IND Safety Reports

The Principal Investigator shall notify FDA via an IND Safety Report of the following information:

- Any AE associated with the use of drug in this study or in other studies that is both serious and unexpected.
- Any finding from tests in laboratory animals that suggests a significant risk for human subjects including reports of mutagenicity, teratogenicity, or carcinogenicity.

The Investigator shall notify his/her IRB/EC promptly of these new serious and unexpected AE(s) or significant risks to subjects.

The Investigator must keep copies of all AE information, including correspondence with Affimed and/or spm² – safety projects & more GmbH and the IRB.

14.8 IND Reporting

During the course of the study, the Sponsor may determine that certain safety reports are required to comply with regulations. The Sponsor is responsible for submission of such reports to their IND. The Investigator may receive a letter called an “IND Safety Report” from this study and/or other Affimed sponsored studies (cross reports). These reports must be submitted to the IRB/EC as required.

Annual IND Report as well as any IND amendments will be reported to the CUMC IRB as well as the FDA.

14.9 Pregnancy

AFM13 might cause harm when administered to a pregnant woman. There are no adequate and well-controlled studies in pregnant women.

Women of childbearing potential will be advised to avoid becoming pregnant while receiving treatment. Women enrolled in this study should either be post-menopausal, free from menses for >2 years, surgically sterilized, or willing to use 2 adequate barrier methods of contraception to prevent pregnancy or agree to abstain from heterosexual activity throughout the study, starting with Visit 1. Women of childbearing potential must have a negative serum pregnancy test (β -hCG) within 7 days prior to receiving the first dose of study drug. Men enrolled in the study must also agree to an adequate method of contraception for the duration of the study.

If a patient or their partner inadvertently becomes pregnant while on study, the patient will immediately be removed from the study and the drugs will be discontinued. Investigators will follow the patient monthly and document the patient’s status until the pregnancy has been completed or terminated. The outcome of the pregnancy will be reported to appropriate parties

within 24 hours if the outcome is an SAE (i.e. death, abortion, congenital anomaly, or other disabling or life-threatening complication to the mother or newborn). If a male patient's partner becomes pregnant on study, the pregnancy will be reported to appropriate parties. Reporting of pregnancy will follow the guidelines outlined in Section 14.3.

14.10 Abnormal Laboratory Values/Vital Signs/Electrocardiograms

Signs and symptoms as well as changes in the laboratory values should be documented in summary as one AE. Unusual laboratory values have to be assessed by the investigator regarding their clinical relevance and – only if they are assessed to be relevant – they have to be documented as an AE. Changes in the peripheral blood count are within the scope of this trial. Therefore, every grade 3/4 anemia, neutropenia, lymphopenia or thrombocytopenia has to be documented as AE.

14.11 Deaths

Should a death occur within the study period or within 60 days after the last administration of study drug an AE form and an SAE form should be completed, detailing the AE that resulted in the death (NB, death is an outcome, not an event). The SAE must be reported to the IRB according to institutional guidelines and FDA within 24 hours. The report should contain a comment regarding the co-involvement of progression of disease, if appropriate, and should assign main and contributory causes of death.

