10.1 Consent and Use of Tissue Specimens for Research

The study ICF will be inclusive for the collection of tumor tissue biopsy and blood specimens for the correlative laboratory research (biological and immunological analyses) will be explained to each patient, and, if willing to participate in this sub-part of the study, must be signed by the patient. The investigator or designee is responsible for explaining and verifying the subject's consent before obtaining any biopsy.

An additional biopsy may be requested from the patient at the EoS visit (4 weeks following the last dose of treatment). This biopsy is optional. Patients are required to undergo skin biopsies of the cutaneous tumor at no more than 6 different time points during the course of the study.

Blood specimens will be obtained from patients for the study of the immunological and biological effects of AFM13. For each patient, the analyses of the peripheral blood will be paired with those of the tumor tissue obtained at the time of the cutaneous biopsies.

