10.7 End of Study Visit

Subjects will return to the study site for an EoS visit after the last treatment or during week 11. At this visit the following will be performed:

- physical examination
- vital signs
- 12-lead ECG
- Optional skin biopsy, if requested by the investigator and agreed upon by the patient
- concomitant medication
- blood sampling for the following:
 - clinical chemistry, hematology and coagulation
 - blood for immunology
 - sCD30
 - ADAs

Patients who discontinue the study for any reason should undergo EoS assessments, if at all possible.

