10.8 Duration of Follow Up

Patients will have an end of study visit after their last dose of drug to evaluate safety. Patients will be further followed every three months by phone call after the 4-week safety evaluation for one year, or until they begin a new treatment for their disease, for evaluation of delayed toxicity. Patients removed from study for unacceptable adverse events will be followed until resolution or stabilization of the adverse event.

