15 STATISTICAL EVALUATION

15.1 Statistical Methods

The data will be analyzed by the Columbia University Medical Center. This is a single center study. The data will be summarized with respect to demographic and baseline characteristics, biological activity measurements, safety observations, efficacy observations, PK and potential biomarker observations. The data will be presented by dose cohorts and overall. The clinical database lock will occur after all data are reconciled (i.e. “cleaned”) for all patients. A single clinical study report will be generated for this study. The Statistical Analysis Plan (SAP) will be finalized and signed before the database lock.

The data analysis will take place after the time of database lock when all patients have completed 2 cycles or discontinued the study prior and all data is cleaned. Further data for patients that are followed up past the two cycles will be summarized in an extension report once all patients have discontinued the study. All analyses are of exploratory nature.

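### SAEs and deaths are reportable for 60 days after the last dose, but a patient who completes a cycle and stops has no scheduled contact in the last 32 to 39 of those days

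*Combined protocol and SAP*

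**What the plan says.** Two sections of the protocol set a 60-day safety window. Section 14.11 (Deaths) requires an AE form and an SAE form "Should a death occur within the study period or within 60 days after the last administration of study drug". Section 14.5 (Recording of Adverse Events) states: "Any new SAEs occurring up to 60 days after the last administration of study drug should be reported". The same section closes routine recording earlier: "Adverse events will be recorded the signing of informed consent until the EOS visit".

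The timing of EoS is given in two ways. Section 10.7 says: "Subjects will return to the study site for an EoS visit after the last treatment or during week 11". Section 10.1 refers to an "EoS visit (4 weeks following the last dose of treatment", and section 10.8 also speaks of a 4-week safety evaluation. After that, section 10.8 has patients "followed every three months by phone call after the 4-week safety evaluation for one year, or until they begin a new treatment". Table 2 shows no contact after EoS.

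Patients who stop drug early come under section 12.9. They have an end-of-treatment visit one week after the last dose and a recommended return at what would have been Week 11. That return is brought forward if new therapy is planned sooner.

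On analysis, section 15.8.1 tabulates AEs recorded during the study, including SAEs and deaths. Section 15.1 says: "The data analysis will take place after the time of database lock when all patients have completed 2 cycles or discontinued the study prior". It adds that the data must be cleaned, and that data on patients followed past two cycles go into an extension report.

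**The concern.** A window in which events must be reported is only as good as the contacts that would reveal them. Here the window runs to day 60, but for a patient who finishes a cycle and stops, the last scheduled visit falls before its midpoint and the next contact falls well after its end. In between, the site learns of an SAE or death only if somebody tells it.

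The gap need not fall evenly. Patients with CR, PR or SD go on to a second cycle, so those who stop at Week 11 of Cycle 1 are mainly progressors. They are the likeliest to start new treatment, and new treatment ends the calls.

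Safety is the first secondary objective, and results are shown by cohort. With three patients in a cohort, one event more or less moves its rate by 1/3, or 33 percentage points. The last three patients planned are an expansion meant to confirm efficacy and tolerability.

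**Working it through.** The plan states no figure for this point, so there is none to reproduce. The check is calendar arithmetic on the protocol's own schedule.

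**Inputs**
- Reporting window: 60 days after the last dose (14.5, 14.11).
- Day 1 of week k is cycle day 7(k − 1) + 1, so Week 8 Day 1 is day 50 and Week 11 Day 1 is day 71.
- EoS: Week 11 (10.7) or 4 weeks after the last dose (10.1, 10.8).
- First call: three months, taken as 91 days, after the 4-week evaluation (10.8).
- Early discontinuers: visit one week after the last dose, then the recommended Week 11 return (12.9).

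**Patient who completes a cycle and stops** (uncovered days = 60 − day of last scheduled visit)
- EoS at Week 11: 71 − 50 = day 21 after the last dose. Uncovered: 60 − 21 = 39 days, and 39/60 = 65%.
- EoS at 4 weeks: day 28. Uncovered: 60 − 28 = 32 days, and 32/60 = 53%.
- First call: 28 + 91 = day 119, which is 119 − 60 = 59 days after the window closes. Counted from day 21 it would be 21 + 91 = day 112.
- Table 2 allows Week 11 restaging ± 2 weeks, so that visit could fall on day 7 to 35, leaving 53 to 25 days uncovered.
- In Cohort 3 the weekly dose ends with a 5-day infusion. If the window is counted from the end of that infusion (day 54 or 55 of the cycle), Week 11 is 17 or 16 days later, leaving 43 or 44 days.

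**Patient who stops early in a cycle**

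The recommended Week 11 return falls 7 × (11 − k) days after a last dose in week k:

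| Last dose in week | 1 | 2 | 3 | 4 | 5 | 6 | 7 |
|---|---|---|---|---|---|---|---|
| Day of Week 11 return | 70 | 63 | 56 | 49 | 42 | 35 | 28 |
| Days of window left | 0 | 0 | 4 | 11 | 18 | 25 | 32 |

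If new therapy brings the return forward, the last contact could be as early as about day 7, leaving 60 − 7 = 53 days (88%).

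**Lock**

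Cycle 2 starts at Week 12, study day 78. Its Week 8 dose falls on 78 + 49 = day 127 and its Week 11 visit on 78 + 70 = day 148. The 60-day window ends on 127 + 60 = day 187, which is 39 days after that visit. Section 15.1 sets no lock date and does not tie lock to the end of this window.

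**Entry into the tables**

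Section 14.5 records AEs to EoS but sends SAEs to day 60 to the safety contractor. Section 15.8.1 counts what was recorded during the study. No sentence says whether an SAE at, say, day 45 is in that count.

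**The case against.** The best case for the plan as written has several parts.

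- **The duty continues.** New treatment ends the calls but not the 60-day reporting duties. Section 14.5 also has an open-ended duty to notify related SAEs that the investigator learns of. This stands, and it rules out saying that progressors lose all contact. They lose scheduled contact. A duty to report what one learns is not a means of learning it.
- **The later call can recover events.** In patients without new treatment, the call at about day 119 can pick up an event from day 29 to 60. This stands: for them the problem is late capture by recall, not loss.
- **Some patients are covered.** The Week 11 return passes day 60 after a last dose in week 1 or 2 and nearly reaches it for week 3. Patients removed for unacceptable AEs are followed to resolution or stabilization, and ongoing AEs are followed for 30 days or longer. This stands in part. The return is only recommended, and the other rules follow known events without asking about new ones. Even a contact at day 30 would leave 60 − 30 = 30 days.
- **Lock need not come early.** Lock also requires cleaned data, and later data have a place in an extension report. So a reader might infer that the last patients will be locked before their windows close, but the documents do not establish that. They only fail to prevent it.
- **Little drug remains and the study is exploratory.** With a half-life of 9 to 19 hours, day 21 (504 hours) is more than 25 half-lives after an infusion, and cohort opening rests on much earlier safety data. That limits the consequence. But the 60-day window is the protocol's own choice and covers SAEs and deaths whatever their cause.
- **Other documents may help.** The Data Safety Monitoring Plan and the DSMB charter are not available here and could contain further follow-up. The finding is limited to what the protocol schedules.

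**Conclusion.** The point holds as a mismatch between a stated reporting window and the contacts that serve it. For a patient who completes a cycle and does not start another, 32 to 39 of the 60 days (53% to 65%) have no scheduled contact, and the first call comes about 59 days after the window closes. This assumes visits on their nominal days and a first call three months after the 4-week evaluation. Early discontinuers are partly covered, unless new therapy moves their last visit forward.

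Events in this stretch are at risk of late capture in patients without new treatment, and of being missed in those who start it. That the latter are mostly progressors is a reasonable inference from the second-cycle rule and the rule ending the calls. The documents give no rates of progression, new treatment or late SAEs, so neither the number of events nor any imbalance between cohorts can be sized. A reader might infer that a cohort with more progression will look safer, or that a given number of events will be lost. The documents support neither statement.

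Whether day-60 events enter the tables, and whether lock waits for them, is left open. This is an inexpensive improvement that should be made. It does not threaten the primary objective.

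**What to change.** - **10.8 and Table 2:** add one phone contact at day 60 (+7 days) after the last dose for every treated patient who has not withdrawn consent, whether or not new treatment has started. Record new SAEs, vital status and the start date of any new treatment.
- **14.5 and 15.8.1:** state that SAEs and deaths up to day 60 are included in the SAE and death tables. The start date of new treatment lets events before and after it be shown separately.
- **15.1:** state that lock follows the last patient's day-60 contact.
- **EoS timing:** reconcile Week 11 with 4 weeks after the last dose, since the uncovered interval depends on it.

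The cost is a small amendment, about 15 calls, and a lock possibly up to about six weeks later: 39 days after the last Week 11 visit on nominal dates, or 39 + 7 = 46 if the call uses its full allowance. Data cleaning may absorb part of that. For early discontinuers whose Week 11 return falls within the day-60 allowance, the two contacts can be combined.
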